6.6.1 Ancillary Imaging study

For 3 to 5 patients, imaging quantitative biodistribution of ^{89}Zr -TLX250 will be evaluated from sequential whole body PET-CT imaging at:

- **D0, dynamic data acquisition during** ^{89}Zr -TLX250 administration.
- **D1 after** ^{89}Zr -TLX250 administration.
- **D3 after** ^{89}Zr -TLX250 administration.
- **D5 after** ^{89}Zr -TLX250 administration.
- **D7 after** ^{89}Zr -TLX250 administration.

6.6.2 Ancillary Biological study

For these 3 to 5 patients, quantitative biodistribution of ^{89}Zr -TLX250 will be evaluated in serum. Blood samples (one heparin tube : 4 ml) will be drawn at:

- **D0 before** ^{89}Zr -TLX250 administration.
- **D0, after dynamic acquisition,** after ^{89}Zr -TLX250 administration.
- **D1 after** ^{89}Zr -TLX250 administration.
- **D3 after** ^{89}Zr -TLX250 administration.
- **D5 after** ^{89}Zr -TLX250 administration.
- **D7 after** ^{89}Zr -TLX250 administration.

Each blood sample will be analyzed for serum ^{89}Zr radioactivity levels in the local nuclear medicine department.

6.7 Independent Central Histological analysis

An independent central histology analysis will be carried out at ICO Saint Herblain. The purpose of this analysis is the determination of the degree of CAIX expression from the biopsy tumor sample.

The degree of CAIX expression will be investigated and classified.

7. SAFETY

ICH requires that both investigators and sponsor follow specific procedures when notifying and reporting adverse events/reactions in clinical trials. These procedures are described in this section of the protocol.

7.1 Definitions

7.1.1 Adverse event Definition

An adverse event (AE) is defined as any untoward medical occurrence, in a patient or clinical trial subject treated by a medicinal product and which **does not necessarily have a causal relationship with this treatment**.

Intensity (severity):

Intensity of adverse events is assessed by the investigator. The intensity criterion should not be confused with the seriousness criterion, which is the guide for defining the reporting requirements.

The intensity of adverse events will be classified according to the NCI-CTCAE Version 5.0.

For any event not listed in this classification, the classification will be assessed as follows:

- **Mild** (grade 1): does not affect the patient's Activities of Daily Living (ADL)
- **Moderate** (grade 2): disrupts the patient's ADL
- **Severe** (grade 3): disabling; limiting self-care ADL
- **Life-threatening** (grade 4): urgent intervention indicated.
- **Death** (Grade 5)

Causal relationship to study drug/procedure:

Relationship between the AE and the study drug /procedure must be assessed following EVCTM (EudraVigilance Clinical Trial Module) criteria: reasonable possibility / no reasonable possibility. Important factors to be considered in assessing the relationship of the AE to study treatment include:

- The temporal sequence from drug/procedure administration
- Recovery on drug discontinuation (de-challenge), recurrence on drug re-introduction (re-challenge).
- Underlying, concomitant, intercurrent diseases.

7.1.2 Definition of serious adverse events

A serious adverse event (SAE) is an AE occurring during any study phase (i.e., screening, run-in, treatment, wash-out, follow-up), at any dose of the study drugs that fulfils one or more of the following criteria:

- **Results in death**

- **Is life-threatening**
- **Requires in-patient hospitalization or prolongation of existing hospitalization**
- **Results in persistent or significant disability or incapacity**
- **Is a congenital abnormality or birth defect in offspring of the patient**
- **Is an important medical event that may jeopardize the patient or may require medical intervention to prevent one of the outcomes listed above.**

The terms disability and incapacity correspond to any temporary or permanent physical or mental handicap that is clinically significant and affects the patient's physical activity and/or quality of life.

Hospitalisations already scheduled before the start of the trial are not considered a serious adverse event.

7.1.4 Unexpected adverse events

An unexpected adverse event (UAE) is an event whose nature, severity, frequency, or course is not consistent with the information about the procedures and methods used in the trial, as defined in the Investigator's Brochure or trial documents.

Reminder: Suspected Unexpected Serious Adverse Reaction (SUSAR) should be reported without delay in the event of death or life-threatening events, or otherwise within 15 days of the sponsor's notification to the competent authorities.

For all SUSARs, the information of follow-up must be submitted in a new delay of 8 days to the Competent Authorities.

7.1.5 New Safety Issue

Any new data that may lead to a reassessment of the benefit/risk ratio of the trial, or that may be sufficiently important to consider changes in the conduct of the study, or trial-related documents, or that may lead to the suspension, termination or modification of the study protocol or similar trial.

7.2 Investigator obligations

7.2.1 Adverse Events reporting

Adverse Events will be recorded in the corresponding section of the e-CRF.

For this study, all adverse events related to ⁸⁹Zr- Girentuximab PET/CT should be recorded in the e-CRF **from the date of administration of ⁸⁹Zr- Girentuximab until 30 days after administration.**

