1.4.4 Benefit / risk balance

There is more than 20 years of experience in humans with SPECT/CT imaging using girentuximab labelled with various radioligands including ¹²⁴I and ¹¹¹In. These studies investigated the pharmacokinetics, toxicity, immunogenicity, and imaging characteristics of radiolabelled girentuximab in kidney cancer patients.

In a clinical phase 1 study investigating safety, tolerability, imaging characteristics, biodistribution and dosimetry, ⁸⁹Zr-TLX250 was found to be safe, and to provide improved imaging characteristics, compared to ¹²⁴I-girentuximab, in line with preclinical findings (44). The clinical development of ⁸⁹Zr-Girentuximab has found the optimal dose of radioactivity to 37 MBq ± 10% of ⁸⁹Zr with a total dose of girentuximab of 10 mg.

Preliminary safety data in the ZIRDOSE study using ⁸⁹Zr-girentuximab, administered ⁸⁹Zr-TLX250 to 5 patients at 5 mg and 10 mg girentuximab mass dose, each, did not prompt any safety concern. In the course of the study, no treatment-related SAEs or SUSARs were reported from any of the 10 patients. A total of 7 AEs were experienced in 4 patients. An unlikely AE or no relationship to treatment was assessed by the investigator for 6 AEs. Mild nausea in one patient was considered by the investigator as possibly related to the study treatment.

In previous ⁸⁹Zr-TLX250 clinical studies, all patients had a whole body PET/CT scan. The CT scans were a low-dose CT for the purpose of attenuation correction of the PET data. Because acquisition parameters for the low-dose CT were restricted, the radiation dose from the low-dose CT was approx. 3 mSv.

Radiation dosimetry was evaluated in a bridging dosimetry study (ZIRDOSE study) investigating the safety and tolerability of ⁸⁹Zr-girentuximab. The whole body effective dose for administration of ⁸⁹Zr-girentuximab in this phase 1 study was 0.487 ± 0.014 mSv/MBq using the most widely

established dose calculation tool OLINDA 1.1 and the ICRP 60 standard (45). The absorbed/effective dose was calculated accordingly and resulted in a total whole body effective dose of 18.0 ± 0.5 mSv for 37 MBq. When a newer software IDAC-Dose 2.1 and the ICRP 103 standard (46) is used, the resulting effective dose will be 0.551 ± 0.030 mSv/MBq or 20.5 ± 1.1 mSv for 37 MBq.

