2.2.2 Endpoints of secondary objectives

1. Percent of positive CA IX metastatic tumor burden compared to total metastatic tumor burden by ^{18}FDG (ratio "Number of positive ^{89}Zr -TLX250 lesions / Number of positive FDG lesions")
2. If a metastasis biopsy is conducted, assessment of the correlation between the normalized uptake values (SUV) of ^{89}Zr -TLX250 positive lesions and CAIX histological expression will be done by comparing the ^{89}Zr -TLX250 semi-quantitative data with the immunohistochemical results (IHC) of biopsied metastases.
3. The safety and tolerability of ^{89}Zr -TLX250 will be evaluated by measuring and monitoring vital signs within 2 hours after injection of the radiopharmaceutical. The patient will be informed that in the event of abnormal physical signs, occurring within 24 hours after ^{89}Zr -TLX250 administration, he must report them to the investigator for

registration. The reporting period of AEs (related to ^{89}Zr -TLX250) and SAEs cover a period of 30 days after ^{89}Zr -TLX250 administration.

- ⇒ The NCI Common Toxicity Criteria, version 5.0 reference will be used.
- ⇒ HACA (Human anti-chimeric antibody) will be assessed.

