If adverse events occur within 30 days post administration, the patient must inform the investigator. These adverse events will be reported in the e-CRF.

6.3.2 ⁸⁹Zr-TLX250 Imaging

On D5 ± 2 days post administration of ⁸⁹Zr-TLX250, a whole body PET/CT imaging will be performed from skull to mid-thigh using 6-8 bed positions with 10 minute acquisition time per bed position.

Laboratory assessments will be performed: Blood count, creatinine clearance, glucose, bilirubin, ALAT, ASAT, Alkaline Phosphatases, and Gamma GT.

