7.2.2 Serious Adverse Events (SAEs) Reporting

7.2.2.1 Reporting information to Sponsor

Any expected or unexpected Serious Adverse Event (SAE) requires the completion of SAE form. The investigator must verify that the information provided on this form is accurate and clear (e.g., do not use abbreviations).

For each reported event, the investigator will complete the SAE Form with at least:

- The patient identification,
- The description of the event, as clearly as possible and in medical terminology,
- The intensity of the event,
- The start and end date of the event,
- The measures taken and whether or not corrective treatment is required,
- If the trial treatment has been interrupted,
- The evolution of the event. In case of a non-fatal event, the evolution have to be followed until the healing or the return to the previous state or the stabilization of possible after-effects,
- The causal relationship between this event and the treatment being tested or a research-related constraint,
- The causal relationship of the event with the treated pathology, another pathology or another treatment.
- The investigator should also attach to the SAE report, whenever possible :
 - ⇒ A copy of the hospitalization report or extension of hospitalization,
 - ⇒ A copy of the autopsy report if necessary,
 - ⇒ A copy of all additional test results performed, including any relevant negative results with the laboratory's normal values,
 - ⇒ Any other document it deems useful and relevant.

All these documents must be anonymized.

All SAE will be followed by the investigator until complete resolution or stabilization (at a level acceptable to the investigator or return to the previous state) even if the patient is out of the trial. A final assessment will be sent to the sponsor.

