7.2.2.3 Notification to the sponsor

The investigator must **immediately (without delay)** and **no later than 24 hours** following knowledge of the event, notify the sponsor pharmacovigilance unit of **any SAE or any new issue** defined in section 7.1.2:

- **from informed consent signature up to $^{89}\text{Zr-TLX250}$ administration:** only SAE related to the study procedures must be reported to the sponsor.
- **from $^{89}\text{Zr-TLX250}$ administration up to 30 days post- $^{89}\text{Zr-TLX250}$ administration:** all SAEs, whether or not related to the study drug/procedure, must be reported to the sponsor.

All delayed Serious Adverse Events (occurring after this period) considered reasonably related to $^{89}\text{Zr-TLX250}$ must be reported without time limit.

Except those that are identified in the protocol as not requiring immediate reporting.

This initial SAE notification shall be followed promptly by a detailed written follow-up report(s) until event resolution.

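### Sections 7.2.1, 2.2.2 and 8.1.4 limit the recording of non-serious adverse events to tracer-related ones, while section 6.3.1 asks for all of them over the same 30 days

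*Combined protocol and SAP*

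**What the plan says.** Three places restrict recording. Section 7.2.1 opens generally, "Adverse Events will be recorded in the corresponding section of the e-CRF", and its next paragraph narrows this for the present study: "all adverse events related to ⁸⁹Zr- Girentuximab PET/CT should be recorded in the e-CRF", from the date of administration until 30 days later. Section 2.2.2 builds the limit into the safety endpoint: "The reporting period of AEs (related to ^{89}Zr -TLX250) and SAEs cover a period of 30 days". Section 8.1.4 repeats that endpoint text. In both, the qualifier is attached to AEs and not to SAEs.

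Other places carry no such limit. Section 6.3.1 says: "If adverse events occur within 30 days post administration, the patient must inform the investigator. These adverse events will be reported in the e-CRF". The schedule of assessments has an AE/SAE row ticked at every visit from screening to day 90. Sections 6.4 and 6.5 call for a review of AEs and SAEs at day 30 and at 3 months. Section 8.8.1 describes the frequency and severity of clinical and biological effects without mentioning relatedness.

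For serious events from administration to day 30, section 7.2.2.3 is explicit: "all SAEs, whether or not related to the study drug/procedure, must be reported to the sponsor". Section 7.2.2.4 lists the exceptions (planned or routine admissions, disease progression and death from progression).

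**The concern.** Secondary objective 3 is to confirm that the tracer's safety and tolerability are perfect. The trial is open-label and uncontrolled (3.1) and has no data monitoring committee (9.1.1). If relatedness decides which non-serious events enter the database, the adverse event table describes attribution, not what happened to the patients, and the filter leans towards the conclusion that the objective already states.

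Attribution is also hard in this population. All patients have metastatic disease. Non-inclusion criterion 2 tolerates grade 1 effects left over from earlier therapy. Criterion 3 bars planned antineoplastic therapy only between injection and imaging. An event put down to another cause and left unrecorded cannot be reassessed later, and a pattern across patients cannot be looked for.

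Because the two rules cover the same window and the same e-CRF, staff following 7.2.1 and staff following 6.3.1 would also build different datasets.

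**Working it through.** The plan states no figure to reproduce here, so the check is mainly a comparison of the rules.

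**Rules side by side**

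| Place | Events | Relatedness condition | Period |
|---|---|---|---|
| 7.2.1 | AEs, to e-CRF | related only | administration to day 30 |
| 2.2.2 and 8.1.4 | AEs | related only | 30 days after administration |
| 6.3.1 | AEs, to e-CRF | none | 30 days after administration |
| Schedule of assessments | AE/SAE | none | screening to day 90 |
| 6.4 and 6.5 | AE and SAE review | none | 30 days and 3 months after the PET scan |
| 8.8.1 | clinical and biological effects | none | 15 days, then 3 months, after the PET/CT |
| 7.2.2.3 | SAEs | none | administration to day 30 |

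Rows 1 to 3 share a window and differ in the set of events. That is the conflict. The table shows a second mismatch: the 8.8.1 windows are not the recording period, and they run from the scan, not from the injection. With the scan at D5 ± 2, 15 days after it is day 18 to 22 after administration (15 + 3 to 15 + 7), and 30 days after it is day 33 to 37 (30 + 3 to 30 + 7).

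**Room for competing causes.** Imaging falls on day 3 to 7. New antineoplastic therapy may therefore start with 30 − 7 = 23 to 30 − 3 = 27 days of the recording window left.

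**Illustration from the earlier study (1.4.4).** Inputs: 10 patients; 7 AEs in 4 patients; one AE, mild nausea in one patient, considered possibly related; for the rest, "An unlikely AE or no relationship to treatment was assessed by the investigator for 6 AEs".

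- Without a filter: 7 AEs, 4/10 patients = 40% (Clopper-Pearson 95% CI 12% to 74%).
- With the 7.2.1 filter: 7 − 6 = 1 AE, 1/10 patients = 10% (95% CI 0.3% to 45%).
- Left out: 6/7 = 86% of events.

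This assumes that the category unlikely in that study maps to no reasonable possibility on this protocol's two-level scale, and that none of the six was serious. Section 1.4.4 gives neither the split between unlikely and unrelated nor the seriousness of those six. Six is therefore the upper end. If all six were rated unlikely and unlikely counted as related, none would be dropped, so the range is 0 to 6.

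**The case against.** The best defence is that the restriction is deliberate. It appears consistently in 2.2.2, 7.2.1 and 8.1.4, and 7.2.1 introduces it as specific to this study. The trial is a single-dose diagnostic pilot, and 1.4.3 cites more than 2000 earlier administrations of radiolabelled girentuximab. Much safety information bypasses the filter: SAEs to day 30, vital signs to 2 hours, day 5 laboratory tests and HACA. All of that stands and limits the point to non-serious events. It does not explain why 6.3.1 gives a different rule for the same window.

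A reader might infer more than the documents support:

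- *That sites would diverge.* Section 3.1 makes the trial monocentric. The divergence would be between staff or between patients.
- *That mild nausea would be missed.* Section 7.1.3 already lists it as expected and related, and it is the one event in 1.4.4 that the filter would have kept.
- *That comparison with the earlier study is lost.* Section 1.4.4 gives both total and attributed counts, so related events can still be compared with related events. Only the all-event comparison goes.
- *That the small sample makes each unrecorded event critical.* Zero events in 12 patients leaves an upper 95% limit of 1 − 0.05^(1/12) = 22.1% one-sided, or 1 − 0.025^(1/12) = 26.5% two-sided. Under the filter that limit concerns related events, and leaving out correctly judged unrelated ones does not alter it. Only misattribution would, and the documents give no rate for that.
- *That the investigator alone decides.* Section 7.1.1 requires relationship to be assessed but does not name the assessor. The SAE form completed by the investigator does ask for "The causal relationship between this event and the treatment being tested or a research-related constraint", so the inference is fair, but it is not the text of 7.2.1.
- *That the AE definition in 7.1.1 contradicts 7.2.1.* It says that an AE "does not necessarily have a causal relationship with this treatment", but a definition does not settle which AEs a trial records.

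**Conclusion.** The conflict is real and should be reconciled. Sections 2.2.2, 7.2.1 and 8.1.4 restrict non-serious AE recording to related events; 6.3.1 does not, and neither do the schedule, the visit reviews or 8.8.1. The word only is implied in 7.2.1, not written, but the shift from its general opening sentence to a rule for this study leaves little room for another reading.

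If 7.2.1 governs, non-serious events judged unrelated are lost for good, and the AE part of secondary objective 3 rests on attribution made before recording. SAEs to day 30 (subject to 7.2.2.4), vital signs, day 5 laboratory tests and HACA are not touched, so it would be wrong to call the whole safety record filtered.

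The size in this trial cannot be forecast. The 6 of 7 events in the earlier study is an illustration from 10 patients and rests on the two assumptions stated with it. Reconciling relatedness alone would still leave the 8.8.1 windows and the day 90 review out of line with the 30-day recording period.

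**What to change.** In 2.2.2, 7.2.1 and 8.1.4, require every adverse event from administration to day 30 to be recorded regardless of relatedness. This agrees with 6.3.1 and with the SAE rule in 7.2.2.3. Keep the two-level causality assessment of 7.1.1 as a separate e-CRF field, and name who completes it. In 8.8.1, tabulate all AEs first and related AEs second: a related list can always be drawn from a complete one, but not the reverse.

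In the same amendment, align the 8.8.1 collection windows (15 days, 3 months) and the day 90 AE review with the recording period, and state whether time runs from the injection or from the scan.

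The cost is a wording change and a few more e-CRF lines for 12 patients who are already scheduled for AE assessment at every visit. The downside is a table that includes background disease events and looks less clean.

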7.2.2 Serious Adverse Events (SAEs) Reporting

7.2.2.1 Reporting information to Sponsor

Any expected or unexpected Serious Adverse Event (SAE) requires the completion of SAE form. The investigator must verify that the information provided on this form is accurate and clear (e.g., do not use abbreviations).

For each reported event, the investigator will complete the SAE Form with at least:

- The patient identification,
- The description of the event, as clearly as possible and in medical terminology,
- The intensity of the event,
- The start and end date of the event,
- The measures taken and whether or not corrective treatment is required,
- If the trial treatment has been interrupted,
- The evolution of the event. In case of a non-fatal event, the evolution have to be followed until the healing or the return to the previous state or the stabilization of possible after-effects,
- The causal relationship between this event and the treatment being tested or a research-related constraint,
- The causal relationship of the event with the treated pathology, another pathology or another treatment.
- The investigator should also attach to the SAE report, whenever possible :
 - ⇒ A copy of the hospitalization report or extension of hospitalization,
 - ⇒ A copy of the autopsy report if necessary,
 - ⇒ A copy of all additional test results performed, including any relevant negative results with the laboratory's normal values,
 - ⇒ Any other document it deems useful and relevant.

All these documents must be anonymized.

All SAE will be followed by the investigator until complete resolution or stabilization (at a level acceptable to the investigator or return to the previous state) even if the patient is out of the trial. A final assessment will be sent to the sponsor.

7.2.2.2 SAE reporting procedure

All SAEs, whether or not related to the study drug/procedure (with the exception of those identified in the protocol as not requiring immediate reporting, see section 7.2.2.4), must be documented and reported to the Sponsor and the study vigilance contact (contact information below).

Completion and reporting procedure:

1. A SAE Form will be completed as precisely as possible, dated and signed by the investigator.
2. This SAE Form must be sent via e-mail to both e-mail addresses below:

[contact] AND [contact]

E-mail title should be completed as follows:

SAE_STUDY name_ddmmmyyyy_site number-patient number_short SAE title with grade

The completed, signed and dated SAE Form should be attached to this e-mail (in pdf format)

3. An acknowledgment of receipt will be kept in the investigator study master file.

7.2.2.3 Notification to the sponsor

The investigator must **immediately (without delay)** and **no later than 24 hours** following knowledge of the event, notify the sponsor pharmacovigilance unit of **any SAE or any new issue** defined in section 7.1.2:

- **from informed consent signature up to $^{89}\text{Zr-TLX250}$ administration:** only SAE related to the study procedures must be reported to the sponsor.
- **from $^{89}\text{Zr-TLX250}$ administration up to 30 days post- $^{89}\text{Zr-TLX250}$ administration:** all SAEs, whether or not related to the study drug/procedure, must be reported to the sponsor.

All delayed Serious Adverse Events (occurring after this period) considered reasonably related to $^{89}\text{Zr-TLX250}$ must be reported without time limit.

Except those that are identified in the protocol as not requiring immediate reporting.

This initial SAE notification shall be followed promptly by a detailed written follow-up report(s) until event resolution.

